#### 6.4.4.2 Primary analyses of neutralization magnitude-breadth curves

##### **Tier 1 Screen of Vaccine Regimens versus Placebo**

The area-under-the-magnitude-breadth curve (AUC-MB) to the tier 1 panel of 3 isolates will be computed for each participant with evaluable neutralization data, as described in [70]. Dunnett’s procedure will be applied with 2-sided alpha = 0.05 to determine which of the  $k = 3$  (Part A) or  $k = 4$  (Part B) vaccine groups have a significantly higher mean AUC-MB than that of the pooled placebo groups, as described in [71] (see their formula (1.1)). This procedure will be applied to construct 95% CIs about the  $k$  differences in mean AUC-MB for each vaccine regimen versus the pooled placebo groups (vaccine –

placebo), which simultaneously have at least 95% coverage probability. The rule for a vaccine regimen passing the tier 1 screen is that the lower confidence limit about the mean difference is above zero. The vaccine regimens passing the tier 1 screen will be advanced to tier 2 evaluation, and regimens failing the tier 1 screen are not planned to undergo evaluation for neutralization of the tier 2 isolates.

#### **Tier 2 screen of vaccine regimens versus placebo**

For the set of vaccine regimens passing the tier 1 screen, the same Dunnett's procedure as described above, using the AUC-MB endpoint for the tier 2 isolates, will be used to determine the set of vaccine regimens that pass the tier 2 screen.

##### 6.4.4.3 Secondary analyses of neutralization magnitude-breadth curves

#### **Superiority comparisons of vaccine regimens passing the tier 2 screen**

For the set of vaccine regimens that passed the tier 2 screen, an F-test will be performed for whether any of the mean AUC-MBs differ. If this test is not significant (p-value  $> 0.05$ ), then the conclusion will be that there were no significant differences in mean AUC-MBs among the advanced vaccine regimens. If the F-test is significant, then simultaneous 95% CIs about the mean-differences in AUC-MBs will be reported. These CIs are computed as the estimated mean-difference plus or minus  $t_{N-m,025}$  multiplied by the square-root of  $S_2$  ( $1/n_i + 1/n_j$ ), where  $t_{N-m,025}$  is the 97.5th percentile of a t-distribution with  $N - m$  degrees of freedom, where  $N$  is the total number of vaccine recipients evaluated (summing over the advanced vaccine regimens) and  $m$  is the number of advanced vaccine regimens. In addition,  $S_2$  is an estimate of the common sample variance of the AUC-MB, whereas  $n_i$  and  $n_j$  are the sample sizes of evaluable participants for vaccine regimens  $i$  and  $j$  being compared. Following Fisher's least significant difference procedure, the pairs of vaccine regimens with this CI excluding zero are deemed to have a significant difference. Nominal (unadjusted) 95% CIs about pairs of vaccine arms will also be reported.

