To test for differences among the vaccine arms in Part A and separately in Part B, first a Kruskal-Wallis rank test or an F-test (depending on the normality assumption) will be used to test for overall differences. Secondly, if the overall test is significant at the 2-sided 0.05 level, then individual tests comparing the 2 adjacent pairs of vaccine arms (Part A) and all 6 pairs of 4 vaccine arms (Part B) will be done unless pre-specified. If rank-based tests are used then the tests will be inverted to construct Hodges-Lehmann point estimates and 2-sided  $(1-0.05/k) \times 100\%$  CIs about the differences in location centers of the  $k = 2$  (Part A) or  $k = 6$  (Part B) pair-wise comparisons of vaccine arms. If actual-value tests are used then the Dunnett's procedure will be used to construct simultaneous confidence intervals about the pairs of mean differences for the many-to-one comparisons [62] when multiple vaccine arms are each compared with 1 common control arm. When all pair-wise comparisons between the multiple vaccine arms are of interest, the Tukey procedure [63] will be used. If only specific comparisons between pairs of the multiple vaccine arms are of interest, the Holm-Bonferroni procedure will be used. An appropriate data transformation (eg,  $\log_{10}$  transformation) may be applied to better satisfy assumptions of symmetry and homoscedasticity (constant variance). Significance of the differences between pairs will be evaluated using 2 procedures, first based on whether the simultaneous 95% CIs exclude zero and secondly based on whether the nominal (unadjusted) 95% CIs exclude zero.

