## Superiority comparisons of vaccine regimens passing the tier 2 screen

Similarly, the  $\max|B_d^G|$  test statistic will be used to compare the distribution of magnitude-breadth curves between each pair of advanced vaccine regimens. The Holm-Bonferroni procedure will be applied to determine the pairs of regimens with significant differences in distribution controlling the family-wise false positive error rate at no more than 0.05. Nominal (unadjusted) 95% CIs about pairs of vaccine arms will also be reported.

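### Section 6.4.4.3 labels its pairwise AUC-MB intervals simultaneous 95%, but the formula gives per-pair intervals with joint coverage of about 80% for four regimens and 88% for three

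*Combined protocol and SAP*

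**What the plan says.** The first subsection of Section 6.4.4.3 begins with an F-test at 0.05 on mean AUC-MB across the regimens that passed the tier 2 screen. It continues: "If the F-test is significant, then simultaneous 95% CIs about the mean-differences in AUC-MBs will be reported". Each interval is the estimated mean difference plus or minus the 0.975 quantile of t(N − m), times the square root of the common variance times (1/n_i + 1/n_j). N counts the evaluated vaccine recipients in the advanced regimens, and m counts those regimens.

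Significance calls use Fisher's "least significant difference procedure, the pairs of vaccine regimens with this CI excluding zero are deemed to have a significant difference". The paragraph ends: "Nominal (unadjusted) 95% CIs about pairs of vaccine arms will also be reported". No formula is given for this last set.

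Two other places show what the plan means by *simultaneous*:

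- In the tier 1 screen of Section 6.4.4.2, the Dunnett intervals are ones "which simultaneously have at least 95% coverage probability".
- In Section 6.4.4.1, significance is judged twice, "first based on whether the simultaneous 95% CIs exclude zero and secondly based on whether the nominal (unadjusted) 95% CIs exclude zero". That section also names a method for this situation: "When all pair-wise comparisons between the multiple vaccine arms are of interest, the Tukey procedure" applies.

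**The concern.** The label and the formula do not match. The plan treats simultaneous intervals as jointly covering at 95% and as distinct from nominal ones. The quantile in Section 6.4.4.3 does not depend on the number of pairs, so it cannot give joint coverage once three or more regimens advance. If the nominal intervals use the same pooled variance, the two promised sets coincide for the advanced pairs, and one table would be printed under two names.

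The screens in Section 6.4.4.2 compare regimens only with placebo. The Section 6.4.4.3 intervals are therefore where differences in mean AUC-MB between sequential, additive and DNA regimens would be read. A reader who trusts the label would expect at least one interval to miss its true difference in one trial in twenty. With four regimens it is about one in five.

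**Working it through.** **Inputs**

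- Up to four vaccine regimens (six pairs) in Part B and three regimens (three pairs) in Part A: Table 3-1.
- 20 per arm in Part B and 12 in Part A, with 10% missing: Section 6.1. Evaluable: 20 × 0.9 = 18, and 12 × 0.9 = 10.8, taken as 11.
- Quantile t(0.975, N − m), pooled variance and the F gate: Section 6.4.4.3.
- Normal AUC-MB with equal variances, as the section's own formula assumes.

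**Joint coverage.** With n per arm, all pairwise intervals cover exactly when the range of the centred arm means, divided by S/√n, is at most √2 × t. Hence

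joint coverage = P(Q(m, N − m) ≤ √2 × t(0.975, N − m)),

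where Q is the studentized range.

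| m | n | df | t | √2 × t | Joint coverage |
|---|---|---|---|---|---|
| 2 | 18 | 34 | 2.032 | 2.874 | 95.0% |
| 3 | 18 | 51 | 2.008 | 2.839 | 87.9% |
| 3 (Part A) | 11 | 30 | 2.042 | 2.888 | 88.0% |
| 4 | 18 | 68 | 1.996 | 2.822 | 80.0% |

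The stated 95% is reproduced only for m = 2, where there is one pair. Without the missing-data allowance (n = 20), m = 4 still gives 80.0%.

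**Robustness.** Simulation agrees with the exact values.

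- Unequal arms with m = 4: 80.0% for sizes 20/18/17/15 and 80.2% for 20/20/20/12.
- 50% or 70% of values at a detection floor (m = 4): 80.1% or 80.9%.
- Variance taken from the two compared arms only: 79.7% (m = 4) and 87.7% (m = 3).

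**Does the F gate help?** Simulated joint coverage given a significant F, n = 18:

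| True means (SD units) | Chance F is significant | Joint coverage given significance |
|---|---|---|
| 0, 0, 0, 0 | 5% | 0% |
| 0, 0, 0, 0.5 | 29% | 58% |
| 0, 0, 0, 1 | 86% | 81% |
| 0, 0, 0, 2 | 100% | 80% |
| 0, 0, 1 | 86% | 89% |
| 0, 0, 3 | 100% | 88% |

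In none of these cases does the gate bring joint coverage to 95%.

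**Quantile that delivers the label.** The Tukey critical value is the 95% point of Q divided by √2.

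- m = 4, df 68: 2.634 against 1.996, ratio 1.32.
- m = 3, df 51: 2.414 against 2.008, ratio 1.20.
- m = 3 in Part A, df 30: 2.465 against 2.042, ratio 1.21.
- m = 2: no change.

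**The LSD significance rule, for context.** Simulated family-wise error of the F-gated rule is 5% with three regimens. With four it is 5% if all are equal, 8% with one regimen 0.5 SD away, 10% with two separated pairs, and at most about 12% when one regimen is clearly different from three equal ones.

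**The case against.** The strongest case is that this is one wrong word in a fully specified secondary analysis. The quantile, degrees of freedom, variance and decision rule are all given and LSD is named, so the analysis can be reproduced as written. Section 6.4 says that secondary endpoints get no formal multiplicity adjustment. Section 6.4.4.1 counts magnitude-breadth AUCs among its quantitative endpoints and plans adjusted pairwise intervals for them. A later subsection of 6.4.4.3 applies Holm-Bonferroni to the advanced pairs, to find "significant differences in distribution controlling the family-wise false positive error rate at no more than 0.05", with a different statistic. The nominal set might also be ungated or cover more arms, and so not be a pure duplicate.

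The trigger may also be rare. At least three regimens must clear a Dunnett procedure that "will be used to determine the set of vaccine regimens that pass the tier 2 screen". In Figure 4-8 all 12 macaques had titers below 20 against tier 2 CH505. Only two reached 22 against tier 2 D.57128, one of them with a MuLV background of 21. Those animals received no DNA, so this is indicative only.

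Much of this stands as a limit on reach, and the headline coverage is a benchmark before the F gate rather than the coverage of the intervals actually printed. It does not rescue the label. The Section 6.4 waiver could justify unadjusted intervals, but not calling them simultaneous. The analyses planned elsewhere do not change what this paragraph reports, and the plan does not say how its sets of intervals fit together. Whether the nominal set covers other arms is left unstated, which is a further reason to clarify.

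**Conclusion.** The point holds. The intervals are per-comparison 95% intervals under a simultaneous label. Before conditioning on the F-test their joint coverage is 80.0% with four regimens, 87.9% with three (88.0% in Part A), and 95% only with two. Conditioning on a significant F does not restore 95% with three or four regimens in any case examined.

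The figures assume normal AUC-MB, equal variances and 10% missing per arm. They barely move with unequal arm sizes, values at a detection floor, or a two-arm variance. The consequence is confined to how a secondary analysis is read when three or more regimens pass the tier 2 screen. Fisher's LSD as a declared rule for significance is not an error, though it does not hold family-wise error at 5% when four regimens advance.

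**What to change.** Settle one of these in the SAP before any unblinded analysis.

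- **(a) Relabel.** Delete *simultaneous* in Section 6.4.4.3 and call these per-comparison (Fisher LSD) 95% intervals. State how the nominal intervals differ in arms, gating or variance, or drop the duplicate. Cost: one word and a clause.
- **(b) Recompute.** If joint coverage is intended, use the Tukey-Kramer quantile for the set labelled simultaneous and keep the present formula for the nominal set. State that the 95% joint coverage is not conditional on a significant F-test. Reword the LSD sentence so that the call refers to the per-pair interval. Cost: about two sentences, and simultaneous intervals 32% wider with four regimens, 20% wider with three (21% in Part A) and unchanged with two.

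Under either option the F-gated LSD rule may stay, described as not controlling family-wise error at 5% with four regimens. The significance calls are unchanged, so no power is lost. Replacing LSD or removing the F gate is optional.

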#### **Omnibus comparison of magnitude-breadth distributions**

The analyses of magnitude-breadth described above are based on the endpoint area-under-the-curve, which is interpreted as the average  $\log_{10}$  IC50 to the set of isolates in the test panel. Use of this endpoint is maximally statistically powerful if 1 vaccine arm has greater magnitude and breadth than the comparator vaccine arm, but may miss an effect wherein 1 vaccine arm has greater magnitude and the comparator vaccine arm has greater breadth. Therefore, a secondary analysis may compare the distribution of magnitude-breadth curves among vaccine arms using the test statistic  $\max|B_d^G|$  from Huang, et al [70] (see page 85), which is designed to detect general differences in magnitude-breadth curve distributions.

#### **Selecting the best vaccine regimen among those passing the tier 2 screen**

For each vaccine regimen that passes the tier 2 screen, the best vaccine regimen will be deemed as that with the greatest value of the  $\max|B_d^G|$  test statistic comparing its distribution of magnitude-breadth curves versus the pooled placebo group.

## Superiority comparisons of vaccine regimens passing the tier 2 screen

Similarly, the  $\max|B_d^G|$  test statistic will be used to compare the distribution of magnitude-breadth curves between each pair of advanced vaccine regimens. The Holm-Bonferroni procedure will be applied to determine the pairs of regimens with significant differences in distribution controlling the family-wise false positive error rate at no more than 0.05. Nominal (unadjusted) 95% CIs about pairs of vaccine arms will also be reported.

### 6.4.4.4 Analysis of CD4+ T-cell response as measured by the ICS assay

The analysis of CD4+ T-cell response rates as measured by the ICS assay will be evaluated and compared as described under the general approach. For each T-cell subset, the positivity call for each peptide pool will include a multiple comparison adjustment for the number of peptide pools used in the assay. In general, the Mixture Models for Single-cell Assays (MIMOSA) statistical framework [72] and/or the Fisher's exact test-based positivity criteria will be used. Details of the positivity criteria will be discussed in the SAP. The magnitude of marginal response will be analyzed as described for quantitative data in the general approach section. For each T-cell subset, graphs will be used to display the background-subtracted magnitudes for each participant by protein, treatment arm and timepoint. When 3 or more cytokines are being measured by the ICS assay, the polyfunctionality of ICS responses may also be analyzed as an exploratory endpoint. Besides descriptive plots of the magnitude of polyfunctional responses, the COMPASS (Combinatorial Polyfunctionality analysis of Antigen-Specific T-cell Subsets) statistical framework may also be used to perform joint modelling of multiple T-cell subsets of different cytokine combinations. For example, the functionality score (FS) and the polyfunctionality score (PFS) may be used to summarize the multi-parameter ICS responses.

### 6.4.4.5 Analysis of multiplexed immunoassay data

When a small panel of analytes (eg,  $\leq 5$ ) is being assessed in a multiplexed immunoassay, the analysis of response rates and response magnitudes will be evaluated and compared as described under the general approach. Details for calculating a positive response and response magnitude will be provided in the SAP. When a larger panel is being assessed, 2 approaches may be considered to evaluate the magnitude and breadth of these responses. First, Magnitude–Breadth (M-B) curves maybe employed to display individual- and group-level response breadth as a function of magnitude. Response breadth of neutralizing antibodies is defined as the average of the  $\log_{10}$  NAb titer over the panel of isolates, where titers that are below the limit-of-detection are set to half of that limit. Response breadth of binding antibodies is similarly defined as the average of the response over the panel of antigens. Two choices are to compare the M-B curves among vaccine arms, as follows: a non-parametric Wilcoxon rank sum test on the subject-specific area-under-the M-B curve (AUC M-B) or a Kolmogorov-Smirnov type test on the 2 group-average M-B curves. Simulations can be used to obtain 2-sided p-values for the latter test. Second, a weighted-average score-like variable may be constructed to account for the correlations between analytes as an integrate magnitude of responses to multiple analytes. Similar group comparison methods described in the first approach may be adopted. Details of either approach will be described in the SAP.

### 6.4.5 Analyses prior to end of scheduled follow-up visits

Any analyses conducted prior to the end of the scheduled follow-up visits should not compromise the integrity of the trial in terms of participant retention or safety or

immunogenicity endpoint assessments. In particular, early unblinded analyses by treatment assignment require careful consideration and should be made available on a need to know basis only.

#### 6.4.5.1 Safety

During the course of the trial, unblinded analyses of safety data will be prepared approximately every 4 months for review by the SMB. Ad hoc safety reports may also be prepared for SMB review at the request of the HVTN 115 PSRT. The HVTN leadership must approve any other requests for unblinded safety data prior to the end of the scheduled follow-up visits.

#### 6.4.5.2 Immunogenicity

An unblinded statistical analysis by treatment assignment of a primary immunogenicity endpoint may be performed when all participants have completed the corresponding primary immunogenicity visit and data are available for analysis from at least 80% of these participants. Similarly, an unblinded statistical analysis by treatment assignment of a secondary or exploratory immunogenicity endpoint may be performed when all participants have completed the corresponding immunogenicity visit and data are available for analysis from at least 80% of these participants. However, such analyses for a secondary or exploratory immunogenicity endpoint will only take place after at least 1 of the primary immunogenicity endpoints of the same class (humoral, cell-mediated, innate or mucosal) or, if no primary endpoint of the same class, at least 1 of the primary immunogenicity endpoints reaches the aforementioned threshold. The Laboratory Program will review the analysis report prior to distribution to the protocol chairs, DAIDS, vaccine developer, and other key HVTN members and investigators. Distribution of reports will be limited to those with a need to know for the purpose of informing future trial-related decisions. The HVTN leadership must approve any other requests for HVTN immunogenicity analyses prior to the end of the scheduled follow-up visits.

## 7 Selection and withdrawal of participants

Participants will be healthy, HIV-uninfected (seronegative) adults who comprehend the purpose of the study and have provided written informed consent. Volunteers will be recruited and screened; those determined to be eligible, based on the inclusion and exclusion criteria, will be enrolled in the study. Final eligibility determination will depend on results of laboratory tests, medical history, physical examinations, and answers to self-administered and/or interview questions.

Investigators should always use good clinical judgment in considering a volunteer's overall fitness for trial participation. Some volunteers may not be appropriate for enrollment even if they meet all inclusion/exclusion criteria. Medical, psychiatric, occupational, or other conditions may make evaluation of safety and/or immunogenicity difficult, and some volunteers may be poor candidates for retention.

Determination of eligibility, taking into account all inclusion and exclusion criteria, must be made within 56 days prior to enrollment unless otherwise noted in Sections 7.1 and 7.2.

### 7.1 Inclusion criteria

#### General and Demographic Criteria

1. **Age** of 18 to 50 years
2. **Access to a participating HVTN CRS** and willingness to be followed for the planned duration of the study
3. Ability and willingness to provide **informed consent**
4. **Assessment of understanding:** volunteer demonstrates understanding of this study completes a questionnaire prior to first vaccination with verbal demonstration of understanding of all questionnaire items answered incorrectly
5. **Agrees not to enroll in another study** of an investigational research agent before the last required protocol clinic visit
6. **Willing to be contacted by phone**, text message, or e-mail 6 months after completion of the scheduled clinic visits
7. **Good general health** as shown by medical history, physical exam, and screening laboratory tests

#### HIV-Related Criteria:

8. Willingness to receive **HIV test results**
9. Willingness to discuss HIV infection risks and amenable to HIV risk reduction counseling.

10. Assessed by the clinic staff as being at “**low risk**” for **HIV infection** and committed to maintaining behavior consistent with low risk of HIV exposure through the last required protocol clinic visit.

### **Laboratory Inclusion Values**

#### **Hemogram/CBC**

11. **Hemoglobin**  $\geq$  11.5 g/dL for volunteers who were born female,  $\geq$  13.0 g/dL for volunteers who were born male
12. **White blood cell count** = 3,300 to 12,000 cells/mm^3
13. **Total lymphocyte count**  $\geq$  800 cells/mm^3
14. **Remaining differential** either within institutional normal range or with site physician approval
15. **Platelets** = 125,000 to 550,000/mm^3

#### **Chemistry**

16. **Chemistry panel:** ALT, AST, and alkaline phosphatase  $<$  1.25 times the institutional upper limit of normal; creatinine  $\leq$  institutional upper limit of normal.

#### **Virology**

17. **Negative HIV-1 and -2 blood test:** Volunteers must have a negative FDA-approved enzyme immunoassay (EIA).
18. **Negative Hepatitis B surface antigen (HBsAg)**
19. **Negative anti-Hepatitis C virus antibodies (anti-HCV),** or negative HCV polymerase chain reaction (PCR) if the anti-HCV is positive

#### **Urine**

20. **Normal urine:**
  - Negative urine glucose, and
  - Negative or trace urine protein, and
  - Negative or trace urine hemoglobin (if trace hemoglobin is present on dipstick, a microscopic urinalysis with red blood cells levels within institutional normal range).

